#### **4.2.3 Main Findings of the Phase II Dose-finding Study in Ivory Coast (MS200661-0005)**

Data from Part 1 of the Phase II study, MS200661-0005, recently completed in African children 2 to 6 years of age infected with *S. mansoni* (using different doses of rac-PZQ ODTs and L-PZQ ODTs as well as reference commercial rac-PZQ arms) showed that L-PZQ 60 mg/kg and L-PZQ 45 mg/kg had the highest efficacy, with cure rates of 90% (95% CI: 79%, 96%) and 86% (95% CI: 74%, 94%), respectively, in the mITT population.

Part II of this study is completed and has enrolled 20 *S. mansoni*-infected children 13 to 24 months of age in Cohort 8 and 4 *S. mansoni*-infected children 3 to 12 months of age in Cohort 9.

Detailed outcomes of the three studies are described in the IB.

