| To assess the safety of a single dose (50 mg/Kg) of L-PZQ ODT in children 4 to 6 years of age infected with S. mansoni (Treatment group 1a) | Safety and tolerability assessments: - Occurrence, nature, severity and outcome of adverse events (AEs), - Occurrence of treatment-related AEs - Changes in laboratory safety parameters (hematology, biochemistry, urinalysis) and vital signs (body temperature, blood pressure and pulse rate) | First treatment to planned End-of-Study visit | 15 |
| To assess the efficacy of a single dose (50 mg/Kg) of L-PZQ ODT as assessed by cure rate 17 to 21 days after treatment, in children 2 to 3 years of age and in infants/toddlers 3 to <24 months of age infected with S. mansoni (Cohorts 2 and 3, respectively) | Same as Cohort 1. | End-of-Study visit | 14.2 |
| To assess the safety of a single dose (50 mg/Kg) of L-PZQ ODT in children 2 to 3 years of age and in infants/toddlers 3 months to < 24 months of age infected with S. mansoni (Cohort 2 and 3, respectively) | Same as Cohort 1. | First treatment to planned End-of-Study visit | 15 |

| Objectives | Endpoints (Outcome Measures) | Endpoints (Outcome Measures) Timeframe | IAP section |
|--|---|--|-------------|

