8.2 Definition of Analysis Populations and Subgroups

Screening Analysis Population (SCR)

The Screening analysis population includes all participants who signed the informed consent.

Intention-to-Treat (ITT)

For the purposes of this trial the ITT analysis set described in the protocol and the safety analysis set described below are considered equivalent. For this reason, the safety analysis set will be utilized for ITT and safety analysis purposes.

Modified ITT Analysis Population (mITT)

The modified ITT (mITT) analysis population will include all enrolled participants who receive one dose of treatment and have baseline measurement. Children who require malaria treatment after enrollment in the study will not be included in the mITT population. The primary analysis of this study will be performed on the mITT population.

Per Protocol Analysis Population (PP)

Per-protocol (PP) Analysis population includes all participants who are in the mITT population and have one post baseline measurement for Cohorts 1, 2, 3 and 4a, and two post baseline measurements for Cohort 4b, without any clinically important protocol deviations. Details of the

criteria for exclusion from the PP population are provided below. An additional determination will be made prior to database lock, based on a review of data accrued during the conduct of the study.

Participants who meet any one of the following criteria will be excluded from the PP:

- Inclusion/exclusion violations
- Subjects that develop withdrawal criteria whilst on the study, but are not withdrawn
- Subjects that receive the incorrect treatment
- Subjects that receive any prohibited medications/foods/fluids as outlined in Sections 5.3, 6.5.2 and 6.5.3 of the protocol;
- Any missed doses of IMP
- Any medical condition that may modify the pharmacokinetic profile of the IMP or compromise the natural immunity of the subject
- End-of-study stool (C1-C3) samples or urine samples (C4) required for assessing the primary endpoint are missing or collected out-of-window

Safety Analysis Population (SAF)

The Safety analysis population will include all participants who receive a dose of study treatment. Participants will be analyzed according to the actual treatment they receive.

Pharmacokinetic Analysis Population (PKP)

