14.2 Secondary Endpoint Analyses

| Analysis (Analysis Population) | Derivation | Statistical Analysis Methods | Missing data handling |
|--------------------------------------|------------|------------------------------|-----------------------|
| CONFIDENTIAL INFORMATION | | | |

| Secondary endpoint: Cure rate 17 to 21 days after treatment, in children 2 to 3 years of age and in infants/toddlers 3 to < 24 months of age infected with S. mansoni (Cohorts 2 and 3, respectively) | | | |
|--|--|---|---|
| Primary (mITT) See 14.2.1 for details about analysis for participant 3 to 24 months of age (Cohort 3). | Same as Cohort 1 (primary analysis). | Same as Cohort 1 (primary analysis). | If the End of Study Kato-Katz egg count is missing, it will be imputed using the Last Observation Carried Forward (LOCF) approach. Subjects with missing data will be considered non-responders. |
| Primary (PP) | | | No Imputation will be done. |
| Secondary endpoint: Cure rate 17 to 21 days and 35 to 40 days after treatment, in children 3 months to 6 years of age infected with S. haematobium (Cohort 4) | | | |

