A total of 65 participants 3 to 24 months of age infected with *S. mansoni* is planned for analysis. Since the sample size in either the Phase II or Phase III study alone is too small to have adequate precision on the cure rate, the results in this Phase III study (MS200661-0003, Cohort 3) will be pooled with Cohorts 8 and 9 of the Phase II study (MS200661-0005, Cohorts 8 and 9). Data that will be pooled for analysis purposes comprises efficacy data, as well as demographics, other baseline characteristics and compliance & drug accountability. Relevant participants' data from the subject-level (ADSL) and efficacy ADaM datasets of the Phase II study (ADLBPARA) will be pooled with the applicable ADaM datasets from the Phase III study (to be prepared). Derived variables will be pooled, directly given that the relevant derivation rules are the same across the two studies. Imputations will be handled in the same way. Efficacy endpoint data that will be pooled from the ADLBPARA dataset from MS200661-0005 include the following:

- Infection intensity data
- Egg counts
- POC-CCA data

For presentation purposes, results from the MS200661-0003 trial will be presented in one table, and then additional tables will be prepared, specifically for participants aged 3 to 24 months, i.e. Cohort 3 from MS200661-0003, and Cohort 8 and 9 from MS200661-0005. These additional tables will be prepared for demographics, other relevant baseline characteristics and all primary and secondary efficacy results.

To align the data from MS200661-0003 the following visits from MS200661-0005 will be used in efficacy analyses:

- Baseline: DAYS -28 TO -1
- FOLLOW UP DAYS 14 to 21 (for analysis purposes this visit will be considered the same as the "DAYS 17 to 21" visit from MS200661-0003)

The definitions of analysis sets including SAF, mITT and PP are the same across the two studies, so the flag for them will not be redrived for the MS200661-0005 participants. The pooled analysis will only apply at the final analysis of the trial data.

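### The pooled infant analysis counts the Phase II Day 14–21 visit as Day 17–21 and imports the Phase II per-protocol flags, so its result may not be a Day 17–21 cure rate

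*SAP*

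**What the plan says.** The infant endpoint in SAP 14.2 is "Cure rate 17 to 21 days after treatment, in children 2 to 3 years of age and in infants/toddlers" (Cohorts 2 and 3). The matching objective in SAP 5 has the same timing.

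SAP 14.2.1 sets out the pooling:

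- The Phase II follow-up visit used is "FOLLOW UP DAYS 14 to 21", and "for analysis purposes this visit will be considered the same as the" Phase III Days 17 to 21 visit.
- "Derived variables will be pooled, directly given that the relevant derivation rules are the same across the two studies".
- "The definitions of analysis sets including SAF, mITT and PP are the same across the two studies", so the Phase II flags are not derived again.
- The additional pooled tables cover all primary and secondary efficacy results. The mapping therefore also reaches egg reduction rate and the POC-CCA result.

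SAP 8.2 excludes a participant from PP if "End-of-study stool (C1-C3) samples or urine samples (C4) required for assessing the primary endpoint are missing or collected out-of-window". The mITT definition (SAP 8.2; Protocol 9.3, Table 6) has no rule on sample timing. Protocol 9.4.1 specifies the pooled analysis on mITT, using a logistic model adjusted for study and site. SAP 14.2 plans PP results for Cohorts 2 and 3 as well.

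**The concern.** The two visit labels, set side by side in SAP 14.2.1, differ by three days at the start, yet they are declared equivalent. Two things follow.

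First, a Phase II result from Day 14, 15 or 16 would be reported as a Day 17–21 result. This is the mITT issue: the label and the mix of sampling times. It is not a difference in exclusions, because mITT excludes nobody for timing.

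Second, the statement that PP is the same in both studies sits uneasily with the labels. A Phase III infant whose first stool is taken on Day 15 is out of window and leaves PP. A Phase II infant sampled on Day 15 is within the labelled visit and may keep a valid PP flag.

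Both documents say that neither study alone gives enough precision in this age group, and the protocol uses the pool to judge whether the effect resembles that in older children. Those older children are scheduled for a first stool at Day 17–21. A difference in timing between studies would be mixed into that comparison. SAP 14.2.1 has no rule based on actual sampling day and no sensitivity analysis for Days 14–16.

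**Working it through.** **Inputs**

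- Planned pool: 65 (SAP 14.2.1).
- Planned contributions: up to 30 and up to 10 from Phase II, at least 25 from Phase III (Protocol 1.1, Number of Participants).
- Actual Phase II enrolment: the study "enrolled 20 *S. mansoni*-infected children 13 to 24 months of age in Cohort 8" and 4 aged 3 to 12 months in Cohort 9 (Protocol 4.2.3, repeated in 9.2).
- Phase III stool timing: first sample Day 17–21, second at most 5 days later (Protocol 8, Follow-up visits).
- Not in the documents: Phase II sampling days, the Phase II PP definition, and cure rates by day of sampling.

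**Reproducing the plan's figure.** 30 + 10 + 25 = 65, as stated.

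**Share that could be affected.** Phase II supplies 20 + 4 = 24. Reaching 65 needs 65 − 24 = 41 from Phase III. The Phase II share is 24/65 = 36.9%. These are enrolment figures; the mITT share could differ slightly.

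**How many were sampled early.** Unknown: 0 to 24. As an illustration, an even spread over the eight days 14 to 21 puts three of eight days before Day 17, giving 24 × 3/8 = 9 infants.

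**Scale of a shift.** Let *k* be the number sampled early and *d* the difference in cure rate, in percentage points, between Days 14–16 and Days 17–21. The pooled rate then moves by (*k*/65) × *d*. Both *k* and *d* are assumptions.

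| Assumed difference *d* | *k* = 9 | *k* = 24 |
|---|---|---|
| 5 points | 0.7 | 1.8 |
| 10 points | 1.4 | 3.7 |
| 20 points | 2.8 | 7.4 |

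For example, 9/65 × 10 = 1.4 and 24/65 × 10 = 3.7. The sign is open: the pooled rate moves whichever way the early results differ.

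**Precision if Phase II is restricted to Day 17–21.** The evaluable pool lies between 41 and 65. With Clopper-Pearson limits and a cure rate assumed near 80%:

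- 52/65 = 80.0%, lower limit 68.2%, distance 11.8 points.
- 33/41 = 80.5%, lower limit 65.1%, distance 15.4 points.

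**PP rules compared.** For a first stool on Day 15, Phase III treats the sample as out of window and SAP 8.2 removes the participant. In Phase II the sample falls inside the labelled visit. Whether Phase II PP followed that label cannot be read from these documents, so the two-window conclusion is conditional.

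**The case against.** The mapping is stated openly and in advance. SAP 14.2.1 also puts this study's results in a table of their own, so an unpooled Cohort 3 rate remains available. Protocol 4.2.5 says the efficacy endpoints match those of Phase II, and cites guidance that measures egg reduction two to three weeks after treatment. Day 14–21 lies inside that interval. The Phase III window is itself nominal, since the second stool may come as late as Day 26 (21 + 5). The analysis is descriptive, with no hypothesis test, and the illustrative 1.4-point shift is small beside a lower-limit distance of 11.8 points.

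Most of this stands and limits the point to a labelling and sensitivity matter. It does not remove it. The cited guidance concerns egg reduction and may make a Day 14–21 window defensible, but the result should then carry that label. The protocol's study-and-site-adjusted model, which SAP 14.2.1 does not repeat, does not turn a Day 15 result into a Day 17–21 result.

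A reader might also infer three stronger things that the documents do not support:

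- *That Phase III discards every sample taken before Day 17.* Only PP has a timing rule, and it removes the participant. An early Phase III sample stays in mITT.
- *That the pooled cure rate is biased downwards.* Neither document gives cure or egg output by day after dosing, so no direction can be claimed.
- *That the pooled PP set certainly uses two windows.* The Phase II PP text is not available here.

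**Conclusion.** The point holds in a limited form. SAP 14.2.1 equates two visits whose labelled windows differ and imports PP flags as identical without checking them against the Day 17–21 window. The pooled infant result may therefore not be a Day 17–21 cure rate. If the Phase II PP window follows its visit label, the pooled PP set also mixes two windows. At most 24 of 65 infants (36.9%) are affected, and possibly none. The 1.4- and 3.7-point shifts rest on an assumed 10-point difference and, for the smaller figure, on evenly spread sampling days. They show scale and are not estimates of bias. This is a secondary, descriptive analysis and the primary endpoint is untouched. The correction is still worth making, because the pool carries the precision for the youngest children and the remedy is inexpensive.

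**What to change.** Make three changes in SAP 14.2.1:

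1. Label the pooled mITT endpoint *Day 14 to 21 (Phase II) / Day 17 to 21 (Phase III)* in the text and in table titles.
2. Replace the statement that PP is the same in both studies with a check of each Phase II infant's first-stool date against the Day 17–21 window. Re-derive the PP flag where the two differ.
3. Add one sensitivity table giving the pooled cure rate with Phase II infants restricted to a first sample on Day 17 to 21.

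The cost is a few lines of SAP text, one derivation from Phase II sampling dates and one table. The downside is that the pooled PP and restricted sets may be smaller and less precise: at the extreme 41 infants instead of 65. If no Phase II infant was sampled before Day 17, the check shows it and the pooled result stands unchanged.

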14.3 Supportive Subgroup Analyses for Efficacy Analysis

Analysis set(s):

- Supportive analyses of the primary endpoint will be based on the mITT and PP analysis sets.

Clinical cure rate by subgroup:

If the End of Study Kato-Katz egg count is missing, it will be imputed using the LOCF approach. Subgroup analyses the study will be performed, by the following subgroups:

- Age category (Cohort 4 only)

- Gender
- Severity of infection
- Country

Descriptive statistics of cure rates for each subgroup will be estimated for each cohort.

Cure rate, in terms of proportion of responders, will be summarised by cohort and by infection severity, gender and country and listed by cohort and subject. Estimates of cure rate will be presented graphically in the form of a forest plots presenting point estimates and 95% CIs, by treatment group and subgroup. Forest plot by age group is needed for Cohort 4 only. Cure rates will be presented as percentages, not proportions, i.e. *cure rate* × 100.

For mITT analysis tables will be presented with imputation and without imputation.

15 Safety Analyses

Safety and tolerability assessments:

- Occurrence, nature, severity and outcome of adverse events (AEs),
- Occurrence of treatment-related AEs
- Changes in laboratory safety parameters (hematology, biochemistry, urinalysis) and vital signs (body temperature, blood pressure and pulse rate)

Analysis set(s):

- SAF analysis set.

Safety analyses will be done on the SAF analysis set and according to the as-treated principle. This section includes specifications for summarizing safety endpoints that are common across clinical trials such as AEs, laboratory tests, reactions to the IMP and vital signs.

15.1 Adverse Events

Details on AEs will be recorded on eCRF page “Adverse Events Details”. Treatment-emergent adverse events (TEAEs) will be defined as those events with onset dates/time occurring after first IMP administration or events that worsen after first IMP administration.

All analyses described in Section 15.1 will be based on TEAEs if not otherwise specified.

If required for an analysis, incomplete date or date/time fields will be imputed as follows:

- Missing start dates will default to the first day of the month and first month of the year, subject to the following exceptions:
 - If an AE start day is missing and month and year is the same as the month and year of IMP administration, then the start day will default to the IMP start day. If the month or year is different, the start day will default to the first day of the month.
 - If start day and month are missing and year is equal to IMP administration year, then the start day and month will be the minimum of IMP administration start date and AE resolution date (AE end date).

- Missing stop dates imputation:
 - If only the day is missing then the last day of the month is used if this does not result in a date after the subject's death in which case the death date will be used;
 - In all other cases the AE end date will not be imputed.
- Unknown times will default to 00:00, subject to the following exceptions:
 - If an AE start time is missing and day and month is the same as the date of IMP administration, then the start time will default to the IMP start time. If the day or month is different, the start time will default to 00:00.
 - If start time, date and month is missing and stop date is not before IMP administration, then the start date/time will default to the IMP start date/time.
 - If start time, date and month and stop date is missing, then the start date/time will default to the IMP start date/time.
- Missing years will not be imputed.

Further information after cut-off (like fatal outcome) might be taken from Safety data base and included separately into CSR.

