#### **Screening**

Children who have tested positive for *S. haematobium* (only) and children who have tested positive for *S. mansoni* (only), together with one of their parents or guardians/legally authorized representatives, will be invited to the study hospital.

Prior to performing any study assessments that are not part of routine medical care, the Investigator or an appropriate designee (if local regulations permit) will obtain written informed consent as specified in [Appendix 2](#) to allow participation in the study and the completion of the study procedures, from one of the parents or a guardian/legally authorized representative of the participant.

Procedures conducted as part of the participant's routine medical care (e.g., blood count) and obtained before signing of the ICF may be used for screening or baseline purposes, provided the

procedures met the protocol-specified criteria and were performed within the time frame defined in the Schedule of Activities (see Section 1.3).

During the screening period, the following tests/information-gathering will be performed within a maximum of one week prior to treatment initiation:

- Clinical safety laboratory evaluations: haematology, biochemistry and urinalysis. All biological assessments will be performed in a fasted condition, if possible, except for breast-fed babies.
- A Rapid Diagnostic Test (RDT) to detect malaria infection (one blood sample collected by finger puncture). This procedure might be performed either in the hospital or in the village, for operational purposes.
- Demographic data, consisting of date of birth, gender and height
- Medical history, including occurrence of seizures, and consisting of all previous diseases considered relevant (relevant is defined as needing medical treatment for at least 1 week) by the Investigator.
- All previous medications received within the last 6 months as considered relevant by the Investigator (relevant is defined as prescribed to treat a relevant disease as described above)
- Complete physical examination (see Section 8.2.2) including body weight
- Vital signs in supine position (see Section 8.2.3) including:
  - BP (systolic and diastolic) – to be assessed at least 5 minutes after resting
  - Pulse rate – to be assessed at least 5 minutes after resting
  - Body temperature. This procedure might be performed either in the hospital or in the village for operational purposes.

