### **8.3.1 Time Period and Frequency for Collecting Adverse Event and Serious Adverse Event Information**

The AE reporting period for safety surveillance begins when the participant is initially included in the study (date of signature of informed consent) and continues throughout the study's post-treatment follow-up period, until the End-of-Study visit. AEs will be captured in the database from the Screening visit up to the End-of-Study visit.

Any SAE assessed as related to study intervention must be recorded and reported, as indicated in [Appendix 3](#), whenever it occurs, irrespective of the time elapsed since the last administration of study intervention.

The method of recording, evaluating, and assessing causality of AEs (including SAEs) and the procedures for completing and transmitting SAE reports are in [Appendix 3](#).

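### An adverse event with only its start day missing is given the dosing day as onset, even when its recorded stop date is before dosing

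*SAP*

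**What the plan says.** SAP section 15.1 (Adverse Events) first defaults an incomplete start date to the first of the month and the first month of the year. It then gives two exceptions.

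- **Only the day missing.** If the "month and year is the same as the month and year of IMP administration, then the start day will default to the IMP start day". No condition is placed on the stop date.
- **Day and month missing, same year as dosing.** In this case "then the start day and month will be the minimum of IMP administration start date and AE resolution date (AE end date". Here the stop date is used.

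The rules for missing times show the same contrast. "If an AE start time is missing and day and month is the same as the date of IMP administration", the time becomes the dosing time, with no stop-date condition. "If start time, date and month is missing and stop date is not before IMP administration", the start becomes the dosing date and time, so this rule does look at the stop date.

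Treatment-emergent events are defined as "those events with onset dates/time occurring after first IMP administration or events that worsen after first IMP administration".

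On collection, Protocol section 8.3.1 states that "AEs will be captured in the database from the Screening visit up to the End-of-Study visit". Protocol section 8 (Screening) has the screening assessments done "within a maximum of one week prior to treatment initiation".

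**The concern.** The order of protection is reversed. A record with its start month known is more complete than one with day and month missing, yet only the less complete record is checked against the stop date. Because collection starts at screening, a child can have an event that begins and resolves before dosing. Protocol section 5.4 foresees such children, since those with a short-lived condition may be enrolled once it clears. For such an event with an unknown start day, the rule overrides a recorded fact, namely that the event was over before the dose.

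Two outputs are at stake.

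- **Listings.** SAP section 9 has imputed values shown in all listings. An onset later than resolution would therefore appear, flagged as imputed, whatever is decided about treatment emergence.
- **Treatment-emergent tables.** If the start time is also missing, as it ordinarily will be when the day is unknown, onset equals the dosing time. If such ties count as treatment-emergent, an illness known to precede the dose is tabulated as following it. If its relationship is missing, SAP section 15.1.1 also counts it as related.

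**Working it through.** The plan gives no figure to reproduce, so the rule was applied literally.

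**Inputs.** The day-only rule, the day-and-month rule and the stop-date rule come from SAP section 15.1. The pre-dose window of up to seven days comes from Protocol section 8 (Screening). The calendar dates are assumed.

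**Worked example.** Dosing 15 October 2020; event start day unknown, October 2020; event end 12 October 2020.

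- Rule as written: onset = dosing date = 15 October. Onset minus end = 15 − 12 = 3 days, so onset falls after resolution.
- With the neighbouring cap: onset = min(15 October, 12 October) = 12 October, which is before dosing and not after the end.

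**Enumeration.** Take every dosing date in 2020 (366 days), every true start from Day −7 to Day −1, and every end from that start to Day −1. Each dosing date has 1 + 2 + … + 7 = 28 start and end pairs, giving 366 × 28 = 10,248 cases. The end date is treated as known and the start day as missing.

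| | Cases | Onset after end, as written | Onset after end, with cap |
|---|---|---|---|
| Start in dosing month | 8,568 | 8,568 | 0 |
| Start in an earlier month | 1,680 | 0 | 0 |
| Total | 10,248 | 8,568 (83.6%) | 0 |

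Every case with its start in the dosing month fails. The other cases default to the first of the earlier month and do not. The 83.6% describes the calendar under equal weighting. It is not an expected share of the trial's adverse events.

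**Where the error stops.** For the stop date, "If only the day is missing then the last day of the month is used". An event in the dosing month with its stop day also missing therefore gets an end at month end, and no inversion arises. The error needs a missing start day, a start month and year equal to those of dosing, and a complete stop date before dosing.

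**Missing time on Day 1.** This was reasoned from the text and not enumerated. If an event on the dosing date has a recorded end time before the dose and no start time, its start becomes the dosing time, again after its end.

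**Size in a table, if ties count as treatment-emergent.** Planned groups of 30 are Cohort 2 and the Cohort 4 children on 50 mg/kg (treatment group 4a). One child is 1/30 = 3.3%. Two children with the same preferred term are 2/30 = 6.7%, above the 5% threshold for the non-serious tables in SAP section 15.1.1.

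**The case against.** The strongest reply is that the definition requires onset after dosing, and an onset equal to the dosing time is not after it. Read strictly, the event stays out of the treatment-emergent tables. That is a fair reading. However, the SAP never says how ties or date-only comparisons are handled, and imputing to the dosing time makes little sense unless such events are meant to count. The effect on these tables is therefore conditional.

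Second, imputation applies only where an analysis needs it, and an event with a known end before dosing can be classified without a start date. This is sensible, but the SAP does not say so. It defines treatment emergence by onset, or worsening, relative to dosing and offers no route through the stop date.

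Third, the situation should be rare. The window is short, and conditions present at the first visit that do not worsen are not adverse events (Protocol Appendix 3). Onset dates are collected, and queries are resolved before database lock. The Day 1 time case is rarer still, because children are in hospital from that morning. All of this stands and limits the size. Passing the 5% threshold would need two such children in one small group with the same preferred term.

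Fourth, the error can only add events and applies to every group alike, and no hypothesis is tested. This also stands. Assigning an event to the dosing day is defensible caution when its timing is unknown. Here the recorded stop date settles the timing, so nothing is gained by overriding it.

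**Conclusion.** The concern holds, with low severity. As written, the day-only rule gives an onset after resolution to every event that starts in the dosing month, has an unknown start day and has a complete stop date before dosing. Nothing found elsewhere in the SAP or protocol adds the missing check. SAP section 11.2 shows the precaution was considered for other data: it does not impute a missing start day and month for medical history that stopped before dosing.

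The impossible date in the listings follows directly from the text. Entry into the treatment-emergent tables depends on ties being counted, and entry into the related-event tables also depends on a missing relationship. The number of affected events is unknown and likely small. Cure rate and egg reduction rate are not affected.

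**What to change.** In SAP section 15.1, extend the minimum already used in the second exception to the first. When only the start day is missing and the month and year match dosing, set onset to the earlier of the dosing date and the event's end date, or to the dosing date if there is no end date. Apply the same cap to a missing start time on Day 1, using the end time where recorded.

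State also that an event with a known end before dosing is never treatment-emergent, and say whether an onset equal to the dosing time counts as after it.

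The cap costs about one sentence and one line of derivation code, and the classification statement adds a short clause. No data collection or trial procedure changes.
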